1.2 Design

This study is a multi-center, randomized, single-blind masking, parallel, two-arm clinical study.

The study duration will be 25-28 weeks (6 months) and will comprise a total of 10 visits: Screening and hygienic phase therapy (weeks -3 to -1), Baseline (week 0), week 2, week 4, week 6, week 8, week 10, week 12, week 16 and week 24 (follow up visit).

During the Baseline visit, eligible patients will be randomized to one of the following treatment regimens:

Treatment 1 – Subgingival debridement + Chlorhexidine Gluconate chip (PerioChip®) inserted every fortnight, for the first 12 weeks.

Treatment 2 – Subgingival debridement.

These treatments will be applied for at least 1 (one) and not more than 2 (two) implants in the oral cavity with clinical and radiographical signs of peri-implantitis. Peri-implantitis is defined as marginal bone loss of at least 3 mm from implant shoulder, and at least 2 mm distal and mesial supporting bone left from the apex to the coronal direction, in combination with bleeding and/or suppuration on probing and a peri-implant Probing Depth (PD) of 5-8 mm.

All pocket measurements (PD, BOP and R) and chip insertions will be made in the same order of procedures every time.

The same examiner will perform all the measurements during the study.

The person (physician/hygienist) placing the Chlorhexidine chips in the periodontal pockets or performing the Subgingival debridement, according to the randomization, will not be involved in target pockets measurements (i.e. the examiner and the physician/hygienist placing the chip or performing the Subgingival debridement will be two different persons).

In each patient meeting the entrance criteria, the deepest periodontal pocket of at least 1 (one) and no more than 2 (two) implant/s (if available) will be selected as a target pocket, and will be used for chip/s insertion or Subgingival Debridement and as the primary efficacy end-point.

The target pocket in the selected implant/s, will be treated at each visit with the same treatment arm, initiated at Baseline visit, as described below.

Implant/s which were not selected as target implant/s will be treated as per the investigators discretion as long as it does not affect the study inclusion/exclusion criteria (e.g. treatment with antibiotics or surgery next to a target implant included in the study).

Treatment 1: (PerioChip®)

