1.8 Sample size

A total of 290 patients will be randomized, in order to analyse at least 123 patients for the Subgingival debridement + PerioChip® arm and at least 123 patients for the Subgingival debridement alone arm. Based on the current drop-out rate (after randomization) of 9%, the expected drop-out rate (after randomization) should be between 12%-15%

Based on previous phase IIa studies, the expected drop-out rate in this study will be between 20%-25%. Thus, it is estimated that approximately 375 patients will be screened in order to randomize up to 290 patients.

The sample size is determined based on relevant literature (Machtei et al. 2012) and previous phase IIa study (CLI/013P) that demonstrated substantial improvement (trend toward significant, $p = 0.07$) in PD reduction between PerioChip® and Placebo chip.

The rationale for sample size calculated is based on detecting a difference of 0.50 mm in PD reduction from baseline between PerioChip® and Placebo chip, with 5% statistical significance and 85% power.

A sample size of 123 in each group will have 85% power to detect a difference in means of -0.50 mm (the difference between a Group 1 mean, of -2.29 and a Group 2 mean, of -1.79) assuming that the common standard deviation is 1.30 using a two group t-test with a 0.05 two-sided significance level.

Statistical significance level for all statistical analysis was set to 5%.

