3.3.1 Principal Analysis

The change in efficacy parameters, PD, during the 24 week treatment, will be modelled using a linear-mixed model (SAS® 9.3 Mixed Procedure) with treatment as fixed factors. Patient and pocket will be entered as random effects. Interactions between treatment and the covariates will be tested and if achieve statistical significance of $\leq 5\%$ will be added to the model as covariate. The analysis will be adjusted to the following covariates known to have influence on the efficacy parameters: age, gender, smoking status, site and baseline measurements. The adequacy of the Mixed Model will be checked and if needed a normalizing transformation will be performed.

Contrasts with 95% C.I. for the difference between the changes by week will be computed.

The Paired T-test or Signed rank test for two means (paired observations) (as is appropriate) will be applied for testing the statistical significance of the decrease in PD at each time point within each study group.

The two-sample T-test or Non-parametric Median test for independent samples (as is appropriate) will be applied for testing the statistical significance of the difference in the PD decrease from baseline between the study groups.

Categorical analysis will be applied for PD change at week 24, using median value calculated overall subjects. Logistic regression will be applied for categorical PD change with adjustment to baseline measure, age, gender, site and smoking status. Interactions between treatment and the covariates will be tested and if found statistically significant, will be added to the model.

Analysis of Variance (ANOVA) will be applied for analysing PD change at week 24, with adjustment to baseline measure, age, gender, site and smoking status. Interactions between treatment and the covariates will be tested and if found statistically significant, will be added to the model.

Missing data will be handled for imputation the primary endpoint data using the MMRM model (Mixed-effect Model for Repeated Measures), which is based on MAR (missing at random) assumption.

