14.3 Safety Data

14.3.1-1	Summary Incidence and Frequency of Adverse Events by Treatment (ITT) (Part 1 of 2)
14.3.1-1	Summary Incidence and Frequency of Adverse Events by Treatment (ITT) (Part 2 of 2)
14.3.1-2	Adverse Events by SOC and PT (ITT)
14.3.1-3	Adverse Events by SOC, PT and relationship to study drug (ITT)
14.3.1-4	Adverse Events by SOC, PT and severity (ITT)
14.3.2	Listings of Deaths, other serious and significant AEs
14.3.2-1	Serious Adverse Events
14.3.3	Other Safety Assessments
14.3.3-1	Oral Inspection and Treatment Results by Visit
14.3.3-2	Pocket Examination at Screening (All pockets, by-patient)

Table number	Table Title
14.3.3-3	Pocket Examination at Screening (All pockets, by-implant)
14.3.3-4	Pocket Examination at Baseline 6-8 mm in depth (All pockets, by-patient)
14.3.3-5	Pocket Examination at Baseline 6-8 mm in depth (All pockets, by-implant)
14.3.3-6	Plaque and Gingival Exam by visit
14.3.3-7	Pregnancy test results by visit
14.3.3-8	Oral Hygiene Instruction by visit
14.3.3-9	Supra-gingival scaling, Supra-gingival plaque removal and Sub-gingival debridement by Visit
14.3.3-10	Chip Insertion by visit
14.3.3-11	Any change in AE since last visit
14.3.3-12	Any dental change since last visit
14.3.3-13	Any change in concomitant medication since last visit
14.3.3-14	Any Concomitant medications

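### Optional efficiency gain: the target pocket's screening PD, read before randomisation, is not a covariate in the principal PD model

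*SAP*

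**What the plan says.** The principal mixed model (SAP 3.3.1) adjusts for "age, gender, smoking status, site and baseline measurements". The last of these terms is plural and is not defined further. The week-24 ANOVA and the logistic model in the same section use the singular. The general model (2.1) and the model under 3.5 also adjust for baseline values, and neither names screening PD.

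Appendix I, under other safety assessments, lists Table 14.3.3-2, "Pocket Examination at Screening (All pockets, by-patient", and Table 14.3.3-3, its by-implant counterpart. No efficacy use of these readings is described.

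Under SAP 1.2, screening and hygienic phase therapy fall in weeks -3 to -1, and randomisation takes place at the baseline visit. The same section says of the deepest pocket of one or two implants: "if available) will be selected as a target pocket". Entry requires a PD of 5-8 mm, and four sites per implant are measured.

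**The concern.** A single probing reading carries error. Where a pocket is chosen because it reads deepest of four, the reading that chose it tends to overstate the true depth, and the 5-8 mm window narrows its range. Both features limit how well one pre-treatment reading predicts the later depth. A second reading of the same pocket, taken before randomisation, helps to separate true depth from reading error and so can lower the residual variance of the week-24 change. It changes neither the endpoint, the estimand nor the patient number. The plan appears to hold such a reading and only tabulate it. What is at stake is some precision in a trial planned at 85% power.

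**Working it through.** **1. The plan's own figure (SAP 1.8).** The target is stated as "A sample size of 123 in each group will have 85% power to detect a difference in means of -0.50 mm". The other inputs come from the same section: mean changes of 2.29 and 1.79 mm, an SD of 1.30 mm in both arms, and a two-sided 5% t-test without covariates.

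- Normal approximation: n = 2 × (1.960 + 1.036)² × 1.30² / 0.50² = 121.4, so 122 per arm.
- Noncentral t: 122 per arm gives 84.9% and 123 gives 85.2%. The stated 123 is therefore right for a t-test.
- Drop-out: 246 / (1 − 0.15) = 289.4, so 290, which also agrees.

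**2. What a second reading adds, by formula.** Let r be the correlation of each pre-treatment PD with week-24 PD (taken as equal for both readings), and r0 the correlation between the screening and baseline readings. With baseline PD already in the model, the residual variance is multiplied by

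[1 − 2r²/(1 + r0)] / (1 − r²).

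This holds for the change as well as for week-24 PD, because baseline PD is in both models. Example with r = 0.5 and r0 = 0.6: (1 − 0.50/1.6) / 0.75 = 0.6875 / 0.75 = 0.917, a fall of 8.3%.

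| r | r0 = 0.5 | r0 = 0.6 | r0 = 0.7 | r0 = 0.8 |
|---|---|---|---|---|
| 0.3 | 3.3% | 2.5% | 1.7% | 1.1% |
| 0.4 | 6.3% | 4.8% | 3.4% | 2.1% |
| 0.5 | 11.1% | 8.3% | 5.9% | 3.7% |

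The documents give neither r nor r0, so no cell can be singled out.

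**3. Simulation with the selection rule.** Assumptions, none of them from the documents:

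- four sites, true-depth SD 1.2 mm, correlation 0.5 between sites, response SD 1.0 mm;
- readings in whole millimetres;
- a mean hygienic-phase fall of 0.2 mm between the two readings;
- the deepest baseline reading is chosen if it is 5-8 mm.

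The slope is that of week-24 PD on true depth. The table gives the fall in residual variance beyond baseline PD.

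| Slope | SD of hygienic-phase effect between pockets | Reading-error SD 0.3 mm | 0.5 mm | 0.7 mm |
|---|---|---|---|---|
| 1.0 | 0 | 5% | 7% | 8% |
| 0.7 | 0 | 2.7% | 3.9% | 4.3% |
| 0.7 | 0.5 mm | 1.5% | 2.7% | 3.5% |
| 0.4 | 0 | 1.0% | 1.3% | 1.5% |
| 0.4 | 0.5 mm | 0.5% | 0.9% | 1.2% |

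A separate simulation with reading-error SD 0.4-0.9 mm and slopes 0.4-1.0 gave 0.7-11.1% when the baseline reading picks the pocket, and 0.5-9.3% when the screening reading does. The gain was positive in every setting.

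**4. What that is worth at 123 per arm** (noncentral t, with 1.30 mm as the starting residual SD):

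| Fall in variance | Fall in SE | Power | n per arm for 85% |
|---|---|---|---|
| 0 | 0 | 85.2% | 123 |
| 0.5% | 0.25% | 85.4% | 122 |
| 2% | 1.0% | 85.9% | 120 |
| 5% | 2.5% | 86.9% | 117 |
| 8% | 4.1% | 88.0% | 113 |
| 11% | 5.7% | 89.0% | 110 |

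**The case against.** **The gain may be negligible.** A gain of 5-8% in the first simulation requires that healing does not depend on depth (slope 1) and that hygienic-phase therapy lowers every pocket alike. The SAP's responder rule asks for 1 mm from a 5 mm pocket and 2 mm from a 6-8 mm pocket, which suggests that deeper pockets are expected to improve more. With slopes of 0.4-0.7 the gain is about 0.5-4%. This stands, and it is why only a range can be given. The simulated SD of change does not help to choose: scenarios worth 0.5% and scenarios worth 8% both sit around 1.30 mm.

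**Screening PD is not a clean replicate.** Hygienic therapy lies between the visits. The interval is 14±7 days for the PP population and unlimited for PP2. This stands. A regression coefficient absorbs a common shift, but a varying one lowers the gain.

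**The power increments are upper-end.** SAP 1.8 uses 1.30 mm as the unadjusted SD for a t-test. Precision already gained from the planned covariates raises the starting power and leaves less to add. This stands.

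**It is not free.** Section 3.3.1 tests the interaction of treatment with each covariate and keeps the significant ones. With six covariates instead of five, and if the tests were independent, the chance of at least one false interaction rises from 1 − 0.95⁵ = 23% to 1 − 0.95⁶ = 26%. This stands unless the new covariate is exempted.

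**The data are not fully described.** A table title does not prove that screening PD is complete for every later target pocket, and the protocol document supplied is a summary of changes. This also stands, so a rule for missing values is needed.

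**Conclusion.** The point holds as an optional, low-cost refinement and not as an error in the plan. The fall in residual variance is about 0.5-8%, at most about 11%, which is about 0.2-4% of SE, at most about 6%. Power at 123 per arm would move from 85.2% to about 85.4-88%, at most about 89%. These figures rest on assumed reading error, healing slope and hygienic-phase effect, and on 1.30 mm as the residual SD.

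A reader might infer four stronger things that the documents do not support:

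- **That baseline PD is the only adjustment.** Age, gender, smoking status and site are also in the model, and the plural baseline term is undefined.
- **That a specific gain such as 5-8% of precision is being lost.** That is one slice of the range, and it refers to variance. A 5-8% fall in SE would need variance to fall by 1 − 0.95² = 9.8% to 1 − 0.92² = 15.4%, near or beyond the top of what was simulated.
- **That baseline PD is known to be the selected maximum.** The SAP does not say which visit's reading picks the deepest pocket. The simulated gain is similar either way.
- **That regression to the mean biases the comparison.** It acts on both randomised arms alike, so the treatment contrast is protected.

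**What to change.** In SAP 3.3.1 (mixed model and week-24 ANOVA) and in the models for the PD secondary endpoints:

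- Prespecify the target pocket's screening PD as a second continuous main-effect covariate beside baseline PD. In by-patient analyses use the mean over the patient's target pockets.
- Exempt it from the treatment-by-covariate interaction screening.
- State a rule for a missing screening value that uses pre-randomisation data only.
- Define which values the baseline term covers, and say which visit's reading selects the target pocket.

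The cost is one degree of freedom, a missing-value rule and a few lines of text, with no new data collection if the screening readings are complete. The change should be made before unblinding. If the screening readings prove largely incomplete for target pockets, leaving the model as it stands loses little.

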2. STATISTICAL METHODS

2.1 General

The change in efficacy parameters, PD, R and RAL during the 24 week treatment, will be modelled using a linear-mixed model (SAS® 9.3 Mixed Procedure) with treatment as fixed factors. Patient and pocket will be entered as random effects. The treatment-by-center interaction will be tested and if achieve statistical significance of $\leq 5\%$ will be added to the model as covariate. The analysis will be adjusted to the following covariates known to have influence on the efficacy parameters: age, gender, smoking status and baseline measurements. The adequacy of the Mixed Model will be checked and if needed a normalizing transformation will be performed. This model will be used for the reduction in PD, R and for improvement in RAL.

Contrasts with 95% Confidence Interval (C.I.) for the difference or ratio between the changes will be computed.

The Paired T-test or Signed rank test for two means (paired observations) (as is appropriate) will be applied for testing the statistical significance of the decrease in PD at each time point within each study group.

The two-sample T-test or Non-parametric Wilcoxon-Mann-Whitney Rank sum test for independent samples (as is appropriate) will be applied for testing the statistical significance of the difference in the percent PD decrease from baseline between the study groups.

Patients may have multiple pockets being treated. All treated pockets will be taken into account to create a by-pocket analysis in addition to the by-patient analysis.

Corresponding 95% C.I. for the difference between treatments not including zero for linear model, or 95% C.I. for the ratios between treatments not including unity for the log-linear regression will prove superior to treatment with PerioChip® versus Subgingival debridement.

Analysis for the number of pockets with at least 1 mm and at least 2 mm reduction in PD, and analysis for BOP for the target implant/s measured at each visit will be analyzed by a Chi-square test or Fisher's exact test as is appropriate.

Logistic regression will be applied for testing the above differences with adjustment to smoking status, Gingival Index (GI), medical center and other suspected confounders, if found. Odds Ratio and 95% Confidence Interval will be calculated using the Logistic model.

Similar mixed models for PD, R and RAL with time as a fixed repeated covariate will be used to reveal the changes of these parameters over time.

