3.5 Exploratory Analysis

- PD, BOP and RAL measurements at week 24 compare to baseline in Responders patients. Responders patients are those patients which demonstrated at week 24 PD reduction of at least 1 mm from baseline PD of 5 mm or PD reduction of at least 2 mm from baseline PD of 6-8 mm inclusive.
- PD and BOP measurements at weeks 8 and 12 compared to baseline.
- Recession (R) and Relative Attachment Levels (RAL) measurements at weeks 8, 12, 16 and 24 compare to baseline.
- PD measurement at week 12 and 16 compared to week 24.
- PD, BOP, RAL and R measured at weeks 8, 12, 16 and 24 for all 4 sites (mesio-buccal, mid-buccal, disto-buccal and mid-lingual), surrounding the selected target implant/s, compared to baseline.

The statistical methods described in the subsequent paragraphs will be used for analysis of both primary and secondary endpoints. The change in efficacy parameters, PD, R and RAL during the 24 week treatment, will be modelled using a linear-mixed model (SAS® 9.3 Mixed Procedure) with treatment as fixed factors. Patient and pocket will be entered as random effects. The interactions between treatment and the covariates will be tested and if achieve statistical

significance of $\leq 5\%$ will be added to the model as covariate. The analysis will be adjusted to the following covariates known to have influence on the efficacy parameters: age, gender, smoking status and baseline measurements. The adequacy of the Mixed Model will be checked and if needed a normalizing transformation will be performed. This model will be used for the reduction in PD, R and for improvement in RAL.

Contrasts with 95% C.I. for the difference between the changes by week will be computed.

The Paired T-test or Signed rank test for two means (paired observations) (as is appropriate) will be applied for testing the statistical significance of the decrease in PD at each time point within each study group.

The two-sample T-test or Non-parametric Median test for independent samples (as is appropriate) will be applied for testing the statistical significance of the difference in the PD decrease from baseline between the study groups.

Patients may have multiple pockets being treated. All treated pockets will be taken into account to create a by-pocket analysis in addition to the by-patient analysis.

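### SAP 3.3.1 and 3.5 name a median test where 2.1 names Wilcoxon on another scale; under the SAP's design assumptions the median test gives up about 18–21 points of power to the t-test

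*SAP*

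**What the plan says.** Three sections of the SAP describe an unadjusted between-arm test of PD decrease.

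- **2.1 General:** "The two-sample T-test or Non-parametric Wilcoxon-Mann-Whitney Rank sum test for independent samples (as is appropriate". The variable is "the difference in the percent PD decrease from baseline between the study groups".
- **3.3.1 Principal Analysis:** "The two-sample T-test or Non-parametric Median test for independent samples (as is appropriate) will be applied". The variable is the PD decrease, without any mention of percent.
- **3.5 Exploratory Analysis:** "The two-sample T-test or Non-parametric Median test for independent samples (as is appropriate", again on the PD decrease. Despite its heading, this section says that the methods it describes serve the primary and secondary endpoints.

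Sections 1.5 and 3.3 define the primary endpoint as the absolute change in PD at week 24. In 3.3.1 the first analysis listed is a linear mixed model adjusted for age, gender, smoking, site and baseline; if it fits poorly, the stated remedy is a normalizing transformation. The t-test or median test follows, together with a logistic regression on a median split and an ANOVA. None of these is labelled primary or supportive, and the condition in brackets that governs the choice of test is never defined.

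**The concern.** A reader cannot tell from the SAP which non-parametric test goes with the t-test, or on which scale. The choice could be made after the data are seen.

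The two candidates are also not equivalent. The median test keeps only whether each value lies above or below the pooled median. Wilcoxon uses the full ordering. If the data are close to the normal model behind the sample size, the median test is clearly the weaker of the two. It could then fail to agree with the mixed model for reasons of power alone, and a report would have to explain a discrepancy that the plan itself created.

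**Working it through.** **Inputs, all from SAP 1.8.** The power statement reads: "A sample size of 123 in each group will have 85% power to detect a difference in means of -0.50 mm". The other inputs there are mean changes of −2.29 and −1.79 mm, an SD of 1.30 in both arms, and a two-sided t-test at 5%.

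**1. The plan's figure.** Power ≈ Φ(δ/σ × √(n/2) − 1.96) = Φ(0.3846 × √61.5 − 1.96) = Φ(3.016 − 1.96) = Φ(1.056) = 85.5%. The exact noncentral t gives 85.2%. The stated 85% reproduces.

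**2. Median test, normal data, by three routes.**
- Asymptotic efficiency 2/π against the t-test: effective n = 123 × 0.6366 = 78.3, so power = Φ(0.3846 × √39.15 − 1.96) = Φ(0.447) = 67.2%.
- Two proportions: the share on the favourable side of the pooled median is Φ(0.25/1.30) = 0.576 in one arm and 0.424 in the other. With 123 per arm the power is 66.9%.
- Simulation of the chi-square median test, 8,000 trials: 64.3%, with a Monte Carlo standard error of √(0.64 × 0.36/8000) ≈ 0.5 point. It is lower because the test is discrete. With 123 of 246 values above the median, the difference in counts d is odd and χ² = d²/61.5. For d = 15 this is 3.66, below 3.84; the first significant value is d = 17 (4.70).

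Loss against the t-test: 85.5 − 67.2 = 18.3, 85.5 − 66.9 = 18.6, and 85.1 − 64.3 = 20.8 points (85.1% is the simulated t-test).

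**3. Wilcoxon, normal data.** Efficiency 3/π: effective n = 117.5, power = Φ(0.987) = 83.8%; simulation 83.5%. The loss against the t-test is 1–2 points. The median test is therefore 83.8 − 67.2 = 16.6 to 83.5 − 64.3 = 19.2 points below Wilcoxon.

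**4. Sample size for the median test.** With proportions 0.576 and 0.424, 85% power needs n = (1.96 × √0.5 + 1.036 × √0.488)² / 0.1525² ≈ 192 per arm, or 384 in all. The SAP randomizes 290.

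**5. Sensitivity to recording resolution and shape.** The documents do not state the recording resolution or the distribution, so these rows are assumptions. All have a 0.50 mm shift and 123 per arm, with 8,000 trials each. The underlying SD is 1.30; rounding is applied afterwards.

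| Shape | t-test | Wilcoxon | Median test | Median − t | Median − Wilcoxon |
|---|---|---|---|---|---|
| Normal | 85.1% | 83.5% | 64.3% | −20.8 | −19.2 |
| Normal, rounded to 1 mm | 83.4% | 81.7% | 61.3–66.0% | −22.1 to −17.4 | −20.4 to −15.7 |
| t with 5 df | 85.3% | 91.5% | 81.9% | −3.4 | −9.6 |
| Laplace | 84.4% | 94.6% | 95.7% | +11.3 | +1.1 |
| Shifted exponential | 85.6% | 99.4% | 82.9% | −2.7 | −16.5 |

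The range in the rounded row reflects how ties and the continuity correction are handled.

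**6. Would a normality test force the switch?** The SAP names no such test. If Shapiro-Wilk were used on normal data, it would reject in about 100% of trials with 1 mm readings, 57–58% with 0.5 mm readings and 5% with continuous values. If by-patient values are means over implants, and half of the patients have two implants with correlation 0.5 (assumptions), 1 mm readings give 92–93% rejection and a median-test power of about 70%.

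**The case against.** The strongest reply has four parts.

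- **The deciding analysis lies elsewhere.** The mixed model comes first in 3.3.1 and is repaired by a transformation, not by a rank or median test. Section 2.1 also ties the superiority claim to a confidence interval from a model, which a median test does not supply. This stands. A reader might infer that the median test becomes the test of the primary endpoint; the SAP does not say so. It is the alternative to an unadjusted t-test only.
- **The loss is conditional.** A fallback is presumably meant for data that are not normal, and there the median test need not lose to the t-test. This also stands: the loss of about 20 points cannot be stated without its assumptions. It does not rescue the choice, because Wilcoxon was better or about equal on every shape tried.
- **The trigger is not in the plan.** One might infer that whole-millimetre readings make the switch almost certain. That needs both a normality test and 1 mm recording, and the documents state neither. With rounded normal data, however, the switch would occur without the change of shape that favours the median test, and the loss would remain.
- **Section 2.1 may describe a different analysis.** Percent decrease could be intended as an extra comparison, so one should not conclude that the word percent is a slip. This stands as a possibility. The SAP does not say so, and percent change appears in none of its endpoint lists.

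**Conclusion.** The inconsistency is in the current SAP text and should be resolved. The sections differ in both test and scale, and nothing says when either applies or what weight it carries.

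Under the design assumptions of SAP 1.8 with normal data, the median test has about 64–67% power, against about 84% for Wilcoxon and 85% for the t-test. That is a loss of about 18–21 points against the t-test and about 17–19 against Wilcoxon. Under the three non-normal shapes tried, the comparison with the t-test runs from a loss of about 3 points to a gain of about 11. The comparison with Wilcoxon on those continuous shapes runs from a loss of about 16.5 to a gain of about 1. Wilcoxon is therefore the better companion to the t-test on what was examined.

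The documents do not support the further claim that the trial's main conclusion would rest on the median test. The effect on the principal inference is nil if the mixed model decides, and the SAP's wording leans that way without stating it.

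**What to change.** - In SAP 3.3.1 and 3.5, replace the median test with the Wilcoxon rank-sum test already named in 2.1, applied to the absolute change in PD.
- In the same places, state that this unadjusted comparison is supportive of the adjusted mixed model and is not selected by a normality test.
- In SAP 2.1, state whether the percent-change comparison is a separate supportive analysis or should read absolute change. Either answer resolves the conflict.

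The cost is SAP wording only; no data collection or sample size changes. On the shapes examined, the downside of Wilcoxon against the median test is about 1 point of power at most (95.7% against 94.6%, continuous Laplace).
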